8.0 DRUG INFORMATION

8.1 0.25% Bupivacaine

- Other names for the drug(s):

Marcaine

- Classification - type of agent:

Anesthetic

- Mode of action:

Sodium Channel blocker

- Storage and stability: Room Temperature

- Protocol dose: 30x2/40mL

- Preparation: None

- Route of administration for this study: Laparoscopic versus percutaneous versus local

- Incompatibilities:

Allergy to local anesthetic

- Availability: Commercially available

- Side effects: Please refer to a complete list of side effects available from the manufacturer

- Nursing implications:

8.1.1 Return and Retention of Study Drug

N/A

7.1.2 Pain scale is asked as part of standard postoperative treatment and is used in order to treat patient's pain.

9.0 CORRELATIVES/SPECIAL STUDIES

N/A

10.0 STATISTICAL CONSIDERATIONS**10.1 Study Design/Study Endpoints**

This is a single-center, single-blinded, (stratified) randomized placebo-controlled three-arm non-inferiority trial with 2:2:1 allocation ratio.

Randomization:

People who meet eligibility requirements and provide informed consent will be randomly allocated to 3 groups to receive either UTAP, LTAP or Placebo with a 2:2:1 allocation ratio. The allocation sequence will be stratified by type of surgery (prostatectomy or partial nephrectomy) using stratified block randomization with randomly varying block sizes. Random permuted blocks sizes within stratification groups will be used to minimize the chance of selection bias. Investigators will be blinded to the size of each block with only the study statistician responsible for generating the randomization list knowing this information. A randomization service called Sealedenvelope.com available at <https://www.sealedenvelope.com/simple-randomiser/v1/> will be used for allocation concealment to ensure that retrieval of the treatment group assignment is only revealed to appropriate team members on a real time basis after each new patient has been screened and consented. This service allows for allocation concealment that would not be possible if the entire randomization list was made available to team members at the beginning of the study. The security and integrity of the codes used by Sealedenvelope.com follows the Food and Drug Administration (FDA) standards for electronic records and follows the International Conference on Harmonisation Good Clinical Practice (ICH GCP) guidelines.

The following is an overview of the randomization generation and management process. The trial coordinator will create an administrator account with sealedenvelope.com. Only the email address given when setting up the trial will be registered as the administrator email address and it can be used to change the password, delete the trial, or receive a list of all randomizations performed at any time. The study statistician will generate the randomization list in Sealedenvelope.com. Once the account for the trial has been opened and the randomization list generated; any designated user (designated by the account administrator) with the single password for the trial can carry out new randomizations. Online randomization is achieved by the user completing a form with the trial ID and password after providing a patient ID as well as surgical type for stratification purposes. An email notification is then generated displaying the next sequential treatment group assignment from the randomization list and sent to the email address given by the user randomizing and the administrator. Data and randomizations held by the sealed envelope randomization system cannot be

changed or edited by users. Sealed Envelope will not edit or delete any data held by the system.

Participants will be blinded from the type of block given. Investigators cannot be blinded due to the nature of the intervention; however allocation concealment will be implemented by use of the sealed envelope service described above.

Blinding:

Participants will be blinded to group allocation throughout the study. Due to the nature of the intervention, it is not possible to blind the investigator to group allocation.

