3.2 Exclusion Criteria

- 3.2.1 Prior Partial Nephrectomy or Subtotal Prostatectomy Surgery (organ specific)
- 3.2.2 Conversion to open surgery
- 3.2.3 History of chronic pain
- 3.2.4 History of opiate or alcohol dependence
- 3.2.5 Allergies to local anesthetic
- 3.2.6 Retroperitoneal surgery
- 3.2.7 Single Port Surgery

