4.0 TREATMENT PLAN**4.1 Treatment Dosage and Administration**

- 4.1.1 30mL of 0.25% bupivacaine will be administered to bilateral TAP using ultrasound or laparoscopic guidance in prostatectomies. 40ml 0.25%

bupivacaine unilateral will be administered in nephrectomy patients (weight based dosage permitting). Placebo groups will receive direct injection of bupivacaine into surgical wounds.

4.1.2 The anesthesia protocol will be at the discretion of the anesthesiologist, including premedication, induction of anesthesia, endotracheal intubation, and maintenance of sedation and neuromuscular blockade. Similarly, all patients will undergo standardized procedure for obtaining pneumoperitoneum and insertion of laparoscopic ports.

Patients in the UTAP group will receive abdominal wall nerve block by the anesthesia team with 30 cc of 0.25% Bupivacaine in bilateral TAP regions under ultrasound guidance (percutaneously) after obtaining general anesthesia. (unilateral 40ml for nephrectomies) Conversely, patients in the LTAP group will undergo bilateral nerve blocks by the surgical team under direct vision from an intraabdominal access after creating pneumoperitoneum and inserting the laparoscope. Patients in the Placebo will receive injection of bupivacaine directly into the surgical wound.

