5.0 STUDY PROCEDURES**5.1 Screening/Baseline Procedures**

Assessments performed exclusively to determine eligibility for this study will be done only after obtaining informed consent. Assessments performed for clinical indications (not exclusively to determine study eligibility) may be used for baseline values even if the studies were done before informed consent was obtained.

All screening procedures must be performed within 0 days prior to registration unless otherwise stated. The screening procedures include:

5.1.1 *Informed Consent***5.1.2 *Medical history***

Complete medical and surgical history, history of infections

5.1.3 *Demographics*

Age, gender, race, ethnicity

5.1.4 *Review subject eligibility criteria***5.1.5 *Review previous and concomitant medications*****5.1.6 *Physical exam including vital signs, height and weight***

Vital signs (temperature, pulse, respirations, blood pressure), height, weight

5.1.7 *Adverse event assessment*

Baseline adverse events will be assessed. See section 6 for Adverse Event monitoring and reporting.

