10.3 Data Analyses Plans

Analysis of Co-Primary Endpoints:

The distribution of VAS pain scores in each group will be examined and assessed for normality and homoscedasticity, visually, by generating probability-probability (P-P) plots, boxplots, stem-and-leaf plots and quantile-quantile (Q-Q) plots, and with the Shapiro-Wilk normality test. If necessary, a transformation of the data will be made to render appropriate for parametric testing. All analyses will be performed on patients who undergo surgery and have a 24 hour VAS pain score assessment. Balance on baseline characteristics (including gender, age at surgery, height, weight, BMI, and operative time) among the randomized groups will be assessed separately for each intervention, using the standardized difference. Any variable with an absolute standardized difference >0.52 (i.e., $1.96 \times 1/n_1 + 1/n_2$) for either intervention will be adjusted for in secondary analyses.^{13,14}

A step-down hierarchical hypothesis testing approach will be used to test the two hypotheses (co-primary endpoints). In the first step, to establish assay sensitivity, the alternative hypothesis that the 24-hour post-operative mean VAS pain score in the UTAP group is superior to that in the placebo group will be tested by a one-sided two sample t-test at the 0.025 level of significance ($H_{01}: \mu_{UTAP} \geq \mu_{Placebo}$ vs. $H_{A1}: \mu_{UTAP} < \mu_{Placebo}$).

If assay sensitivity is demonstrated in the first step by rejecting the null hypothesis, H_{01} , we will proceed to the second step of testing for non-inferiority of LTAP to UTAP. To establish non-inferiority, the alternative hypothesis that LTAP is non-inferior to UTAP will be tested using the ‘fractional approach’ introduced by Pigeot et al (2003) where the effect estimate is based on the ratio of the differences in means between LTAP and placebo and UTAP and placebo ($H_{02}: \frac{\mu_{LTAP} - \mu_{Placebo}}{\mu_{UTAP} - \mu_{Placebo}} \leq \theta$: vs. $H_{A2}: \frac{\mu_{LTAP} - \mu_{Placebo}}{\mu_{UTAP} - \mu_{Placebo}} > \theta$).

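### Section 10.1 lets unblinded staff learn the arm before premedication, induction and the final decision to operate, although no arm needs it before general anaesthesia

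*Combined protocol and SAP*

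**What the plan says.** **When the arm becomes known.** Section 10.1 states: "People who meet eligibility requirements and provide informed consent will be randomly allocated to 3 groups". The assignment is "only revealed to appropriate team members on a real time basis after each new patient has been screened and consented", and it is emailed to the person who randomises and to the account administrator. Section 5.1 adds: "All screening procedures must be performed within 0 days prior to registration unless otherwise stated". That ties screening to registration. Nothing ties registration, or retrieval of the assignment, to the day of surgery, to induction or to the start of the operation.

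**Who knows it.** Participants are blinded. For staff, Section 10.1 says: "Due to the nature of the intervention, it is not possible to blind the investigator to group allocation".

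**What is still open before the block.** Section 4.1.2 says: "The anesthesia protocol will be at the discretion of the anesthesiologist, including premedication, induction of anesthesia". The same anaesthesia team gives the UTAP block.

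**When each arm needs it.** UTAP is given "under ultrasound guidance (percutaneously) after obtaining general anesthesia". LTAP follows pneumoperitoneum and insertion of the laparoscope. The control injection goes into the surgical wound (all Section 4.1.2).

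**Who is analysed.** Section 10.3: "All analyses will be performed on patients who undergo surgery and have a 24 hour VAS pain score assessment". No analysis of all randomised patients and no missing-data method is given. Section 4.8 separately removes patients who die, are converted to open surgery or return to the operating room.

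**The concern.** Central allocation with varying block sizes protects the order of assignment at enrolment. It does not protect the interval between learning the arm and giving the block. In that interval staff who know the arm can choose premedication and induction, and can influence whether the case goes ahead. A case that does not go ahead leaves the analysis.

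Section 10.1 justifies unblinding by the nature of the intervention, but that reason applies only from the block onward. The plan gives no reason for allowing the arm to be known sooner.

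What is at stake is the second-step ratio. Lower VAS is better, so anything that lowers the LTAP mean for reasons other than the block raises the apparent retained fraction and makes a false non-inferiority claim more likely.

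**Working it through.** **Inputs (Section 10.2).** Means (variances): LTAP 1.49 (1.77), UTAP 1.49 (1.77), placebo 3.40 (1.50). Sizes 94, 94 and 47. One-sided alpha 0.025, power 90%. Assumed UTAP effect 3.40 − 1.49 = 1.91 cm. Retention fraction θ is 0.50 in the text and 0.70 in the printed software call.

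**Step 1: the plan's own sample size.**

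N = (1.960 + 1.282)² × [1.77/0.4 + θ² × 1.77/0.4 + (1 − θ)² × 1.50/0.2] / [(1 − θ) × 1.91]²

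- θ = 0.70: N = 232.6, or 235 in whole 2:2:1 blocks. Power at 235 is 90.3%. The plan's figure reproduces.
- θ = 0.50: N = 85.3. Power at 235 is 99.97%. The plan's figure does not reproduce.

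The two values of θ must be reconciled, but that is a separate matter. The check below is done at both.

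**Step 2: standard error of the non-inferiority contrast.**

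SE = √[1.77/94 + θ² × 1.77/94 + (1 − θ)² × 1.50/47]

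- θ = 0.50: √(0.01883 + 0.00471 + 0.00798) = 0.1775
- θ = 0.70: √(0.01883 + 0.00923 + 0.00287) = 0.1759

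**Step 3: error at the boundary if the LTAP mean is lowered by b cm.** The documents give no value for b, so these values are assumptions. Error = Φ(b/SE − 1.96).

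| b (cm) | Rise in retained fraction, b/1.91 | Error, θ = 0.50 | Error, θ = 0.70 |
|---|---|---|---|
| 0 | 0 | 2.5% | 2.5% |
| 0.1 | 0.05 | 8.1% | 8.2% |
| 0.2 | 0.10 | 20.2% | 20.5% |

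The direction is also assumed. A shift of 0.2 cm against LTAP would instead reduce power, to 98.9% at θ = 0.50 or 56.4% at θ = 0.70. With no dependence on arm there is no bias.

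**Step 4: how much selective loss such a shift would need.** Suppose a share p of LTAP patients is lost before surgery, none is lost elsewhere, and those lost would have scored d = 2 cm higher. The shift is p × d/(1 − p). The SE is held at its planned value.

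- p = 2%: 0.041 cm, error 4.2% (θ = 0.50)
- p = 5%: 0.105 cm, error 8.6%
- p = 10%: 0.222 cm, error 23.9%

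This is a severe assumption: 2 cm exceeds the whole assumed UTAP effect of 1.91 cm and is about 1.5 standard deviations (2/1.33).

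**Step 5: power if losses are unrelated to arm.** With 10% of the 235 dropped, power is 87.1% at θ = 0.70. At θ = 0.50 it stays above 99.7% even with 20% dropped.

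**The case against.** A reader might infer more than the documents support.

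- **That the arm is in fact released before premedication.** Section 10.1 gives an earliest time only, in a passage explaining why the list is not handed out at the start. Retrieval after induction would also comply. This objection stands: the defect is that early release is permitted, not that it is prescribed.
- **That the operation is undecided at release.** Section 3.0 requires all criteria to be met at registration, without waivers. Section 3.2 lists "Retroperitoneal surgery" and single-port surgery as exclusions, and Section 10.1 requires the type of surgery to be entered before an assignment issues. The planned approach must therefore be known. What remains open is whether the case goes ahead and whether the plan changes.
- **That patients switched to an excluded approach are dropped.** No text says so. Read literally, Section 10.3 keeps one who has a 24-hour VAS.
- **That there is a long gap before surgery.** Section 11.3 puts participant involvement at no more than one week, which suggests a short gap. It does not place release after premedication.
- **That bias has been shown.** Nothing in the documents suggests that block type affects whether an operation proceeds or which premedication is chosen. Participants, who score the VAS, are blinded, and Section 4.3 sets out postoperative pain medication. Those safeguards act after the block, not before it.
- **That later release would cure the losses.** Conversion, return to the operating room and a missing VAS remove patients whenever the arm is revealed. Maintenance of anaesthesia is also discretionary and follows the reveal in any case.

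What remains is an avoidable period of unblinding for which the plan gives no reason.

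**Conclusion.** The point holds as a cheap improvement to the design. The plan permits staff to know the arm earlier than any arm requires, while anaesthetic choices and the decision to proceed are open, and its analysis set leaves out those who then have no surgery.

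The size is unknown. The rise from 2.5% to about 8% or 20% rests entirely on an assumed shift of 0.1 or 0.2 cm in favour of LTAP, and it is nearly the same at either value of θ. It shows how sensitive the ratio test is, and it is not an estimate of bias in this trial. Loss of power is not a material part of the point at the stated θ of 0.50.

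**What to change.** In Section 10.1, keep consent and screening beforehand, and replace the release condition with wording such as: *The assignment is retrieved from the online service in the operating room after induction of general anaesthesia, once the surgeon has recorded that the planned operation and approach still meet Sections 3.1 and 3.2, immediately before the UTAP block would be given. A patient counts as randomised from that point. Losses after it are reported by arm, with reasons.*

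The surgeon's record cannot cover conversion to open surgery, which Section 3.2 lists as an exclusion but which is known only during the operation. Those losses, returns to the operating room and missing 24-hour VAS scores need their own handling in Sections 4.8 and 10.3.

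**Cost.** The change is to protocol wording, since the service already releases assignments in real time. Block equipment must be available for every study case, and retrieval may add a little time in the operating room. Operating room time is a secondary endpoint (Section 2.4), and avoiding the time for a separate ultrasound block is part of the rationale (Section 1.4). Block set-up should therefore start only after a UTAP assignment, so that the comparison of operating room time is not diluted.

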10.2 Sample Size and Accrual

For two-arm non-inferiority trials, issues such as choice of non-inferiority margin, constancy assumption, and assay sensitivity have been debated for years, and the statistical methodology has been challenged. Three-arm trials including the experimental treatment, an active reference treatment and a placebo are recommended in the guidelines of the ICH⁵ and EMEA/CPMP⁶ as a useful approach to the assessment of assay sensitivity providing the trial with internal validation. The placebo group affords an opportunity to test for non-inferiority directly without use of a fixed pre-specified non-inferiority margin thereby making the constancy assumption an irrelevant point and allows for direct testing of assay sensitivity by comparing the active reference to the placebo.

The objectives of this trial are two-fold: 1. to verify assay sensitivity by demonstrating that UTAP (the active reference) is superior to placebo at controlling 24 hour postoperative pain and 2. to demonstrate non-inferiority of LTAP (the experimental approach) to UTAP (the active reference) with respect to 24 hour postoperative pain control.

A step-down hierarchical hypothesis testing approach will be used to test the two hypotheses (co-primary endpoints). In the first step, to establish assay sensitivity, the alternative hypothesis that UTAP is superior to placebo will be tested:

$$H_{01}: \mu_{UTAP} \geq \mu_{Placebo}$$

$$H_{A1}: \mu_{UTAP} < \mu_{Placebo}$$

If and only if we reject the null hypothesis, H_{01} , thereby establishing assay sensitivity will we proceed to the second step, to demonstrate non-inferiority of LTAP to UTAP.

In the second step, to establish non-inferiority, the alternative hypothesis that LTAP is non-inferior to UTAP will be tested using the 'fractional approach'

introduced by Pigeot I et al (2003) where the effect estimate is based on the ratio of the differences in means between LTAP and placebo and UTAP and placebo⁷ :

$$H_{02}: \frac{\mu_{LTAP} - \mu_{Placebo}}{\mu_{UTAP} - \mu_{Placebo}} \leq \theta$$

$$H_{A2}: \frac{\mu_{LTAP} - \mu_{Placebo}}{\mu_{UTAP} - \mu_{Placebo}} > \theta$$

θ is a pre-specified fixed fraction of active reference effect (retention of effect). Koch and Tangen⁸ provide reasonable regions of θ for non-inferiority testing between 0.5 and 0.99.

If the null hypothesis, H_{02} is rejected for a given θ , we will claim that LTAP (the experimental approach) retains more than $\theta \times 100\%$ efficacy of UTAP (the active reference) compared with the placebo, and non-inferiority of LTAP to UTAP will be declared.

With a hierarchical step down closed testing procedure (which can occur when one has two or more endpoints for which demonstration of an effect on each is needed to support regulatory approval), the familywise type I error rate is controlled at the level α as there is only one way to succeed, however, the type II error rate is inflated thereby decreasing the overall power to show success on both endpoints. To account for inflation of the type II error rate, the sample size will be calculated to provide an overall power (to detect both endpoints) of 80% by setting the power for each hypothesis test at 90% ($90\% \times 90\% = 80\%$)⁹ corresponding to $\beta=0.10$.

The statistical methodology for a test problem based on the ratio of (differences in) population means was published by Koch et al. (1998).¹⁰ The null hypothesis H_{02} , referred to above as our second hypothesis, can be rejected, if the lower limit of Fieller's one-sided 100 $(1-\alpha)\%$ confidence interval for the ratio of differences in means is greater than θ . Pigeot et al. (2003) investigated Fieller's confidence interval and derived formulas for power and hence sample size calculation. The R package 'ThreeArmedTrials' developed by Tobias Muetze (2016)¹¹ provides a collection of functions for statistical inference in three-arm trials using the formulas derived by Pigeot et al. for a normally distributed outcome. For a study assessing non-inferiority of an experimental approach compared to an active reference, tools to: determine optimal sample size allocation among groups (UTAP, LTAP, Placebo), compute total (and group) sample size required to detect a particular non-inferiority fraction θ at a particular power and alpha level, as well as analyze the final data set are provided. For a normally distributed endpoint the group means, variances as well as power, alpha, group allocation ratios and non-inferiority fraction θ need to be specified for computation of sample size. It is recommended by Muetze to use estimates of means and variances from a random effects meta-analysis of the historical placebo-controlled trials comparing UTAP to placebo (presented in Section 1.1). Based on meta-analysis of the four

historical placebo-controlled trials with parameters listed in the table below and discussed in the introduction, the estimated pooled mean pain scores and (total variance) was 3.4 (1.50) in the placebo and 1.49 (1.77) in the UTAP groups. The random effects meta-analysis was conducted with the Comprehensive Meta-Analysis Software Version 3.3.070 (2013).¹²

Study name	Treatment	Mean	SD	Variance	Sample size
Hosgood (2012)	Placebo	3.70	2.00	4.00	22
Aniskevich (2014)	Placebo	4.00	2.30	5.29	11
Qu (2016)	Placebo	2.80	1.20	1.44	40
Fabrizio (2018)	Placebo	3.57	0.64	0.41	50
Random	Placebo	3.40		1.50	
Hosgood (2012)	UTAP	1.90	1.50	2.25	24
Aniskevich (2014)	UTAP	1.50	1.20	1.44	10
Qu (2016)	UTAP	0.84	0.59	0.35	40
Fabrizio (2018)	UTAP	1.80	0.82	0.67	50
Random	UTAP	1.49		1.77	

In accordance with ICH guidelines on statistical principles for clinical trials a type I error rate of 0.025 was used for this sample size calculation. Optimal sample size allocation was determined to follow a 2:2:1 ratio of LTAP:UTAP:Placebo. A total sample size of 235 is required with a 2:2:1 allocation ratio (94 LTAP, 94 UTAP and 47 Placebo) to achieve 90% power to establish non-inferiority of LTAP to UTAP with a fixed fraction of 0.50 (LTAP has to achieve more than 50% of the effect of UTAP compared to placebo to claim as non-inferior) assuming means and variances of 1.49 (1.77), 1.49 (1.77) and 3.40 (1.50) in the LTAP, UTAP and Placebo groups, respectively. This sample size calculation was performed using the PowerRet function of the 'ThreeArmedTrials' package with the following parameters:

```
power_RET(experiment = c(1.49,1.77), reference = c(1.49,1.77), placebo = c(3.4,1.5),Delta = 0.7, sig_level = 0.025, power= 0.9, allocation = c(2,2,1)/5,distribution = "normal")
```

The statistical evaluation will be performed in the first step by a two sample t-test for demonstrating superiority of UTAP over placebo. Group sample sizes of 94 and 47 for UTAP and placebo groups achieve over 99% power to reject the null hypothesis of equal or worse means when the population VAS pain score means (SDs) in the UTAP and Placebo groups are 1.50 (1.33) and 3.4 (1.22), respectively, with a significance level of 0.025 using a one-sided two-sample unequal-variance t-test. The calculation was performed with PASS Version 15.

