θ is pre-specified as the fixed fraction of active reference effect (retention of effect) of 0.50 (LTAP has to achieve more than 50% of the effect of UTAP compared to placebo to claim as non-inferior). The second step will be carried out based on the Fieller’s one-sided 97.5% lower confidence bound for the ratio of $\mu_{LTAP} - \mu_{Placebo}$ and $\mu_{UTAP} - \mu_{Placebo}$. If the lower bound of the confidence interval is greater than 50% then the null hypothesis, H_{02} is rejected (LTAP (the experimental approach) retains more than 50% efficacy of UTAP (the active reference) then non-inferiority of LTAP to UTAP will be declared. The formula for calculating Fieller’s confidence bound is presented in Pigeot et al (2003) and will be implemented using The R package ‘ThreeArmedTrials’ developed by Tobias Muetze (2016).

Analysis of Secondary Endpoints:

The secondary endpoints of 24-hour cumulative post-operative opioid analgesic requirement expressed in morphine equivalent dose (MED), intraoperative time taken to complete the surgical block, total operating room time and surgical time will be summarized using median, 1st and 3rd quartiles and minimum and

maximum values. A Kruskal-Wallis analysis of variance will be used to compare the cumulative MED requirement (time to complete the surgical block, total operating room time and surgical time) among the three intervention groups with all pairwise comparisons made between groups using the Dwass-Steel-Critchlow-Fligner procedure (Dwass 1960; Steel 1960; Critchlow and Fligner 1991).¹⁵⁻¹⁷

The secondary endpoint of antiemetic medication use will be reported as the number and percentage of patients that require antiemetic medication during their hospital stay within each intervention group. A Chi-Square will be used to compare percentages across groups. A log-binomial regression model will be used to estimate and compare the prevalence ratios (PR) and corresponding 95% confidence intervals (CI) for antiemetic medication use among patients in the three intervention groups.

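### Overall power is not the stated 80%: step 1 is near certain, so overall power equals step 2 power, about 90% or about 99.97% depending on which of two conflicting retention fractions applies

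*Combined protocol and SAP*

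**What the plan says.** All of this is in section 10.2 (Sample Size and Accrual) unless noted.

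- **Testing order.** Step 1 tests UTAP against placebo. Step 2 tests whether LTAP retains more than a fixed fraction θ of the UTAP effect. Step 2 is reached "If and only if we reject the null hypothesis" of step 1.
- **Power target.** The size is to give an "overall power (to detect both endpoints) of 80% by setting the power for each hypothesis test at 90" per cent, with the product 90% × 90% = 80% given as the reason.
- **Step 2.** A total of 235 (94 LTAP, 94 UTAP, 47 placebo) is said to give 90% power "with a fixed fraction of 0.50", "assuming means and variances of 1.49 (1.77), 1.49 (1.77) and 3.40 (1.50) in the LTAP, UTAP and Placebo groups". The software call printed directly below has Delta = 0.7.
- **Step 1.** Groups of 94 and 47 are said to "achieve over 99% power to reject the null hypothesis of equal or worse means".
- **Decision rule (section 10.3, Data Analyses Plans).** The step 2 criterion begins "If the lower bound of the confidence interval is greater than 50% then the null hypothesis", so it uses 0.50.

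The plan never combines its own two step-wise figures into an overall power.

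**The concern.** The product rule gives 80% (strictly 81%) only if both tests have 90% power and are independent. Section 10.2 itself reports that step 1 has over 99%. If step 1 almost never fails, the hierarchy costs no power, and the chance of succeeding on both hypotheses is the chance of succeeding on step 2.

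Overall power for the two co-primary hypotheses is a headline property of the design, and the reason given for setting step 2 at 90% rests on it. The true figure also cannot be read off the page, because step 2 power depends on the retention fraction and the plan gives two values for it.

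**Working it through.** **Inputs, all from sections 10.2 and 10.3.** Means (variances): LTAP 1.49 (1.77), UTAP 1.49 (1.77), placebo 3.40 (1.50). The UTAP–placebo difference is 3.40 − 1.49 = 1.91. Allocation is 2:2:1, so the shares are 0.4, 0.4 and 0.2. On alpha, "a type I error rate of 0.025 was used for this sample size calculation", and section 10.3 specifies a "one-sided two sample t-test at the 0.025 level of significance" for step 1. For step 1 the means (SDs) are 1.50 (1.33) and 3.4 (1.22).

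**1. Reproduce the planned size for step 2.** For the retention-of-effect test with unequal variances, the normal approximation is

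N = V(θ) × (z₀.₉₇₅ + z_power)² / [(1 − θ) × 1.91]², where V(θ) = 1.77/0.4 + θ² × 1.77/0.4 + (1 − θ)² × 1.50/0.2.

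- θ = 0.7: V = 4.425 + 2.168 + 0.675 = 7.268, and the squared effect is 0.573² = 0.3283. For 90% power, N = 7.268 × 10.507 / 0.3283 ≈ 233.
- θ = 0.50: V = 4.425 + 1.106 + 1.875 = 7.406, and the squared effect is 0.955² = 0.9120. For 90% power, N = 7.406 × 10.507 / 0.9120 ≈ 86 (85.3 rounded up).

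With a noncentral t distribution (Satterthwaite degrees of freedom, N in multiples of 5) the sizes are 235 and 90. The planned 235 therefore comes back exactly at θ = 0.7. At 0.50 no variant tried reaches it; the largest, which misreads the variances as SDs, gives 146.

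**2. Step 1 power at 94 versus 47.** SE = √(1.33²/94 + 1.22²/47) = √(0.01882 + 0.03167) = 0.2247. The difference of 1.90 is 1.90/0.2247 ≈ 8.5 standard errors, so power exceeds 99.99%.

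**3. Step 2 power at N = 235.**

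- θ = 0.7: SE = √(7.268/235) = 0.1759; 0.573/0.1759 − 1.960 = 1.298. Power is 90.3% by the normal approximation and 90.0% by t.
- θ = 0.50: SE = √(7.406/235) = 0.1775; 0.955/0.1775 − 1.960 ≈ 3.42. Power is about 99.97% by either method.

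**4. Joint power at N = 235.** A simulation of 200,000 trials, with the UTAP and placebo arms shared between the two tests, gave these results:

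| θ | Step 1 | Step 2 | Both |
|---|---|---|---|
| 0.7 | >99.99% | 90.1% | 90.1% |
| 0.50 | >99.99% | 99.97% | 99.97% |

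**5. Size for 80% overall, for scale only.** At θ = 0.7 it is about 174 (normal) to 180 (t); a simulation at 175 gave 79.7%. At θ = 0.50 it is about 64 (normal) to 70 (t). Step 1 power is still about 99% at a total of 65 to 70, so the dominance of step 2 is not peculiar to 235.

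**The case against.** The best defence is that 80% is a planning floor, not a claim about achieved power. Two tests with at least 90% power each must jointly have at least 80%, whatever their correlation, and section 10.2 then reports the steps separately. As mathematics this stands, and 80% versus 81% is rounding. It does not rescue the text. The plan does not call 80% a bound; it says the size is calculated to provide that power by setting each test at 90%, and its own step 1 figure shows that step 1 was not set there.

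It is also fair to say that little turns on the error. True power is above the stated figure, the type I error is unaffected and no analysis changes. That stands, and it makes this a minor correction.

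A reader might go further and infer that the trial is oversized by about a third and should be cut. The documents do not support that. The ratio, 235/180 ≈ 1.31 to 235/174 ≈ 1.35, holds only at θ = 0.7. At 0.50 it is 235/70 ≈ 3.4 to 235/64 ≈ 3.7. No excess can be stated until the fraction is settled.

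Nor can one infer that 90% in step 2 buys nothing. At θ = 0.7 it raises joint power from 80% to 90%. It also absorbs losses for which section 10.2 makes no allowance, although section 10.3 analyses only patients with a 24-hour score and section 4.8 removes patients who are converted to open surgery or return to the operating room. At 0.7, a fall from 235 to 180 analysed patients (55/235 ≈ 23%) would still leave 80%.

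**Conclusion.** Wrong as written. On the plan's own inputs overall power at 235 equals step 2 power: about 90% at the printed Delta of 0.7, or about 99.97% at the 0.50 of the sample-size text and decision rule. Under neither is it 80%. The statement that 235 gives 90% step 2 power at a fraction of 0.50 is wrong on the same calculation; that fraction needs only about 86 to 90 patients for 90%.

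These figures assume the plan's means and variances, equal LTAP and UTAP means, normally distributed scores and a 24-hour score for all 235 patients. The conclusion that step 2 governs overall power does not depend on the choice of fraction; the figure to report does. The conflict between 0.50 and 0.7 is therefore the larger matter and has to be resolved first.

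**What to change.** 1. Reconcile the retention fraction across the section 10.2 text, the printed software call and the section 10.3 decision rule.
2. Delete the product 90% × 90% = 80% and the sentence that derives the overall power from it.
3. State that step 1 power exceeds 99.9% at 94 versus 47, so overall power equals step 2 power, and give that figure for the reconciled fraction: about 90% at 0.70, or about 99.97% at 0.50.
4. Correct the sentence that pairs 235 and 90% power with a fraction of 0.50, so that fraction, size and power agree.

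The cost is a short amendment to section 10.2, and to section 10.3 if the reconciled fraction differs from the one in the decision rule. Restating the power changes neither the testing procedure nor enrolment.
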